Context: Craniosynostosis is a common craniofacial abnormality which can be associated with various clinical syndromes. Though it has been established that children with craniosynostosis score lower on certain developmental tests, the effect of craniosynostosis and cranioplasty surgery on the neural circuitry and brain development is less well known or understood.

Objectives: The purpose of this study is to describe the effect of cranial vault remodeling in children with craniosynostosis on white matter tracts with tractography and Diffusion tensor imaging (DTI), functional MRI, and neurodevelopmental tests, before and after surgery as compared to age-matched controls.

Study Design: This will be a prospective study of patients diagnosed with craniosynostosis and who are going to have open or endoscopic cranial vault remodeling (CVR).

Study Measures: The study will measure MRI sequences before and after surgery and at set time intervals to quantify the effect of white matter tract maturity. Parallel to this, neurodevelopmental tests will be administered at these same intervals.

Background and Rationale

Introduction

Craniosynostosis, the premature ossification and fusion of one or more cranial sutures, is a common craniofacial abnormality occurring in 1 of 2,000 live births.^{1 2} Craniosynostosis can lead to increased intra-cranial pressure in between 12-50% of those affected which may have delayed neuro developmental implications.

The crucial neurodevelopment occurs in the first years of life and is most rapidly progressing during the first year of life. Premature closure of the cranial sutures decrease the intracranial volume and space available for the rapidly developing brain. Cranial vault remodeling (CVR) is the current standard of care to mitigate any possible developmental delay secondary to craniosynostosis and also improve the head shape. CVR is a combined surgery between the neurosurgeon who takes off the cranial bone/bones, and the craniofacial surgeon who assists and reconstructs the cranium with absorbable plates and screws.

After surgery, although there is no doubt that there is an improvement in head shape, the craniofacial skeleton and the soft tissues, but there is less data, and virtually no functional imaging information available addressing the effect of CVR surgery on the growing brain.

Title: Neurodevelopmental Outcomes in Craniosynostosis Repair
PI: [name]
Site: Arkansas Children's Hospital
Funding: UAMS Intramural Grant

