- Approximately 60 age-matched **controls** (3 in each group) not diagnosed with craniosynostosis syndrome, stratified by age groups starting at 3 months, 5 months, 7 months, 9 month 11 months, 13 months, 15 months, 17 months, 19 months, then every 3 months, 22 months, 25 months, 28 months, 31 months, 34 months, 37 months, 40 months, 43 months, 46 months, 49 months.

Title: Neurodevelopmental Outcomes in Craniosynostosis Repair
PI: [name]
Site: Arkansas Children's Hospital
Funding: UAMS Intramural Grant

Exclusion Criteria

- Children not meeting the inclusion criteria
- Children with traumatic brain injury, brain cancer, or VP shunt that could affect development.
- Children who have already undergone CVR repair
- **Developmentally Normal children who cannot undergo or cannot be still for an awake or asleep non-sedated MRI**

Study Design and Procedures

This observational study intends to collect all available patient data, including but not limited to:

- Age
- Date of birth
- Sex
- Race
- Ethnicity
- Physical Examination
- Personal Medical History
- Family Medical History
- Presenting clinical status
- Craniosynostosis type
- Present surgical history and procedures
- Inpatient Progress notes
- Discharge summaries
- Clinic notes
- Other interventions
- All Laboratory Results
- All Imaging Results
- Neurodevelopmental Assessments

Title: Neurodevelopmental Outcomes in Craniosynostosis Repair
PI: [name]
Site: Arkansas Children's Hospital
Funding: UAMS Intramural Grant

Radiological Component

Standard-of-care at ACH and at other institutions is initial imaging to confirm the diagnosis of craniosynostosis and identify any other intra-cranial abnormalities. This initial imaging can be in the form of either a low-dose radiation computed-tomography (CT) of the head or a MRI. Post-operative imaging, either CT or MRI, is based on clinical indicators and not routinely performed on all patients. Once the patient is identified and consented for the study, we will implement an MRI-based protocol to look at both the bone and the brain, thus obviating the need for a CT scan, however, in some cases a CT scan may need to be obtained or have been obtained at an outside facility.

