Presurgical MRI will be done on a 3T MRI (Prisma Siemens MRI scanner) or 1.5T (Achiva, Phillips MRI scanner). The protocol for patients less than 18 months of age will be Sagittal T1, Axial inversion recovery (IR), T2, fluid-attenuated inversion recovery (FLAIR), susceptibility weighted image (SWI), diffusion weighted images (DWI), diffusion tensor imaging (DTI), resting state fMRI, and sagittal 3D GRE / FFE (on 1.5 T scanners) or 3D T1 VIBE (on 3T scanner).

The MRI protocol for patients over 18 months of age will be: Sagittal T1, coronal T2, Axial T2, fluid-attenuated inversion recovery (FLAIR), susceptibility weighted image (SWI), diffusion weighted images (DWI), diffusion tensor imaging (DTI), resting state fMRI, and sagittal 3D GRE / FFE (on 1.5 T scanners) or 3D T1 VIBE (on 3T scanner).

Post-processing of the acquired 3D GRE, FFE and T1VIBE sequences will be done on vitrea station. The acquired images will be reviewed by US board-certified pediatric neuroradiologists for single or multi suture craniosynostosis. Intracranial volume, ventricular size and sulcal crowding will be accessed. The DTI data will be analyzed on a password protected workstation by MRI physicist (Co-investigator, [name] and his research assistant, [name]) for evaluation of white matter microstructural integrity. Other imaging data from the same MRI sequences may also be exported to the workstation for additional quantitative analysis.

The expected time for MRI image acquisition is approximately 60 minutes for control subjects. If this process is prolonged greater than 2 hours due to control subject's lack of cooperation or discomfort then it will be aborted and will be re-scheduled. If the parents do not wish to proceed with a rescheduled time then the control subject will be removed from the study.

The MRI protocols will be identical for the control subjects and scheduled at the parent's convenience, but falling within one week on either side of their requested age. Because scheduling of the MRI may not allow this degree of control, control patients will be stratified by the age when they actually undergo the study not the age of recruitment. We will not plan to sedate the normal control subjects, however, sedation *may be a*

Title: Neurodevelopmental Outcomes in Craniosynostosis Repair
PI: [name]
Site: Arkansas Children's Hospital
Funding: UAMS Intramural Grant

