sedation, if and only if non-pharmacologic techniques do not produce a state in which the radiologist ([name]) thinks a high-quality image can be generated. Our team will attempt the non-sedation techniques first and if a child does need sedation to successfully complete the imaging study, the following risks will apply and be explained in the consent to the parents including: administration of medications for anesthesia including inhaled sevoflurane, intravenous propofol which have known side effects of nausea, vomiting, tachycardia, respiratory obstruction, hemodynamic instability, cough or laryngospasm. In addition other known complications of using a controlled airway, i.e., laryngeal mask airway (LMA) for children > 1 year old and endo-tracheal tube for < 1 year old, include tooth or mucosal injury, malignant hyperthermia, allergic reaction to an agent given.

There is also the risk associated with putting in performing intravenous (IV) access and these risk are typically infiltration of saline or anesthetic agents such as propofol into the skin or hematoma and/or bruising. There is also a risk of multiple sites puncture wounds, if a child if intra-venous access proves difficult. If for whatever reason the imaging study can not be performed within a reasonable parental expectation then the child will not be included in the study, but continue clinical care regardless.

All these common risks will be explained to the parents and if a side-effect or complication occurs, all treatment will be administered by the anesthesia team and the study coordinator and PI's will be notified and the IRB through our data-safety monitor within 24 hours of occurrence.

The potential risk of the MRI itself is the risk of causing anxiety in the patients and families and we plan to adopt the following measures borrowed from the techniques described from the investigators of the NIH funded Baby Connectome Project ¹³ for non-sedated MRI included but not limited to a tour of the MRI area prior to the scheduled MRI to familiarize the child and parents with the scan experience, prepping the parents with the headphones the child will wear, use of attenuating foam on the scanner, sandbags to reduce vibrations, dim lights, and pre-selected movies for the awake scans for the child.

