Title: Neurodevelopmental Outcomes in Craniosynostosis Repair
PI: [name]
Site: Arkansas Children's Hospital
Funding: UAMS Intramural Grant

plan to analyze data both for quality control and preliminary analysis every 6 months while the study is on-going.

Statistical Methods

For the complex analysis of large amounts of MRI data on the same patient and comparing with other patients, we plan to employ biostatistical support baseline and demographic characteristics will be summarized by standard descriptive summaries (e.g., means and standard deviations for continuous variables such as age and percentages for categorical variables such as gender).

Data will be presented as frequencies, medians with ranges, or \pm SD, as appropriate. Tests of group differences will include the paired t-test, χ^2 , and z-test, as appropriate. Repeated measures analysis will also be performed to on pre- and post-operative data for the same patient.

DTI parameters will be computed by standard software and will be compared between patients and controls or between different ages using standard statistical methods. Of note, for each MRI session, whether or not the participant was sedated will be a variable including in analysis.

Ethical Considerations

This study will be conducted in accordance with all applicable government regulations and Arkansas Children's Hospital research policies and procedures. This protocol and any amendments will be submitted and approved by the UAMS Institutional Review Board (IRB) to conduct the study.

The formal consent of each caregiver for their child, using the IRB-approved consent form, will be obtained before that subject is submitted to any study procedure. The caregivers of all subjects for this study will be provided a consent form describing this study and providing sufficient information in language suitable for subjects to make an informed decision about their participation in this study. The person obtaining consent will thoroughly explain each element of the document and outline the risks and benefits, alternate treatment(s), and requirements of the study.

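### For fMRI, the one scan-state variable named for analysis (sedated or not) codes sleeping and awake-with-movie runs alike, so uncontrolled pre- to post-operative change may be confounded with state

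*Combined protocol and SAP*

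**What the plan says.** - **Objectives** (opening summary): the study is to describe the effect of surgery using "Diffusion tensor imaging (DTI), functional MRI, and neurodevelopmental tests, before and after surgery as compared to age-matched controls".
- **Radiological Component**: the sequence lists for children under and over 18 months both contain "diffusion weighted images (DWI), diffusion tensor imaging (DTI), resting state fMRI". Controls have the same MRI protocol and are not planned to be sedated.
- **Exclusion Criteria**: developmentally normal children are excluded if they "cannot be still for an awake or asleep non-sedated MRI". An unsedated scan can therefore be made in either state.
- **Risks and Benefits**: the list of calming measures ends with "dim lights, and pre-selected movies for the awake scans for the child". It names no sequence for which the movie is stopped. If these measures fail in a patient, the same section describes "administration of medications for anesthesia including inhaled sevoflurane, intravenous propofol".
- **Statistical Methods**: "for each MRI session, whether or not the participant was sedated will be a variable including in analysis". No other scan-state variable is named.

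**The concern.** A functional run made while a child watches a movie is driven by a stimulus. A run in natural sleep is not, and a run under anesthesia is a third condition. The plan allows all three, calls the sequence resting state, and names a variable that separates only the third from the other two.

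Children enter at 3 to 24 months and stay until 4 years of age, so every pre/post pair spans a large change in age. If infants are mostly scanned asleep and older children more often awake with a movie, the mix of states shifts between visits even when nobody is sedated. An apparent change in functional connectivity after surgery could then be a change in how the child was scanned. If state is not noted at the scanner, it may not be recoverable later.

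**Working it through.** The plan gives no fMRI sample size, effect size or state mix, so there is no stated figure to reproduce. The check has a logical part and an illustration on assumed values.

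**1. What the yes/no variable separates**

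| State at the run | Who | Code under the plan |
|---|---|---|
| Natural sleep | patients, controls | not sedated |
| Awake with movie | patients, controls | not sedated |
| Anesthetized | patients only, by plan | sedated |

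Among unsedated runs the variable is constant, so adjusting for it cannot remove any sleep-versus-movie difference. The sedation effect itself can be estimated from patients alone.

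**2. Size among unsedated runs**

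Let *p* be the rise in the awake-with-movie share between two visits and *d* the awake-versus-asleep shift in SD units. With no true change, the spurious change is *p* × *d*. Both are assumptions.

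- Smallest on the grid: 0.3 × 0.2 = 0.06 SD.
- Middle: 0.7 × 0.5 = 0.35 SD.
- Largest: 0.9 × 0.8 = 0.72 SD.

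For *d* = 0.2, 0.5 and 0.8, a rise in awake share from 10% to 50% (*p* = 0.4) gives 0.08, 0.20 and 0.32 SD. A rise from 10% to 90% (*p* = 0.8) gives 0.16, 0.40 and 0.64 SD.

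**3. With group, age and sedation in one model**

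A large simulated data set (400,000 runs, half patients) had true group and age effects of zero. Assumptions:

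- age uniform over 3 to 49 months;
- chance of being awake following a logistic curve centred at 26 months with scale 6 months;
- among patients, 10% of would-be sleepers and 60% of would-be awake children sedated; no controls sedated;
- sedation effect −0.5 SD, residual SD 1.

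Least squares on group, age and sedated yes/no gave:

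| *d* (SD) | Spurious group effect (SD) | Spurious age slope (SD per year) |
|---|---|---|
| 0.2 | −0.03 | 0.05 |
| 0.5 | −0.06 | 0.13 |
| 0.8 | −0.09 | 0.21 |

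The age slope carries most of the artefact. The smaller group effect arises because sedation takes would-be awake patients out of the unsedated class. For example, at an age where half would be awake, unsedated patients are 0.5 × 0.4 = 0.20 awake and 0.5 × 0.9 = 0.45 asleep. Their awake share is 0.20 / 0.65 = 0.31, against 0.50 in controls. At *d* = 0.5 the gap at that age is (0.31 − 0.50) × 0.5 ≈ −0.10 SD.

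Adding the sleep/movie split brings both spurious effects to about 0. That follows from how the data were generated. It shows that the missing split is the cause, but says nothing about precision at the study's real numbers.

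**The case against.** **The plan specifies no fMRI analysis.** The aims and the three listed endpoints concern DTI and white matter, the only imaging parameters named in Statistical Methods are DTI parameters, and the imaging data to be pooled across sites are from the DTI analysis. This stands, and it limits the point to the functional MRI objective. A reader might infer that the DTI endpoints are compromised; nothing here shows that. The absence of an fMRI outcome or model is a related gap that the fix below does not close.

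**Two steps are readings of the text.** A reader might infer that the movie certainly plays during the fMRI run. The document attaches movies to awake scans in general and makes no exception, so this is a reasonable reading but not a statement. A reader might also infer that nothing but sedation is recorded. Statistical Methods says what enters the analysis, not what is noted at the scanner.

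**The link between age and state is not documented.** This also stands. The awake-or-asleep wording comes from a criterion for developmentally normal children, and no section gives the mix for unsedated patients. The calming list does single out awake scans, which implies that others are not.

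**Age matching protects the group contrast.** Largely true. If state follows age, matched controls under the same MRI protocol share much of the mix, and the illustration gives a group artefact of no more than 0.09 SD in absolute value. Aim 2 also compares patients with controls. A reader might infer that patient-control contrasts are as exposed as pre/post change; the documents do not support that. Pre/post change without controls remains exposed.

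**Stronger remedies would do harm.** Comparing only runs in the same state could leave few pre-operative to age-4 pairs, with three controls per age group and no sedated controls. Stopping the movie would remove a calming measure in a protocol where failure of calming leads to sedation. Neither is recommended.

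**Conclusion.** The point holds for the functional MRI objective. Sleeping and awake-with-movie runs share one code, and no adjustment for sedated yes/no can tell them apart. Whether this biases uncontrolled pre- to post-operative change depends on the awake share changing with age and on state affecting the chosen measure. Both are plausible; neither is in the documents. The size is therefore unknown: 0.06 to 0.72 SD over the assumed grid, which runs from negligible to large. The effect on age-matched patient-control contrasts is likely smaller. The change is still worth making because state may not be recoverable afterwards and costs little to capture.

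**What to change.** For each fMRI run, record state at the scanner as one of four levels: natural sleep, awake with movie, awake without movie, sedated. In Statistical Methods:

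- use this variable in place of sedated yes/no in any fMRI analysis;
- report state by group and visit;
- add a same-state sensitivity analysis where numbers allow;
- do not label movie runs as resting state;
- state that sedated patient runs have no planned control counterpart.

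Make no change to calming or sedation practice.

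The cost is one extra REDCap field per scan and less precise fMRI estimates. Where state and age overlap little, the coding will have limited power to separate them. With three controls per age group, state has to be modelled across ages, and the report should say so.

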Craniosynostosis may be characterized as simple (involving 1 suture) or complex (involving two or more sutures), primary (caused by an intrinsic defect in the suture) or secondary (premature closure of normal sutures because of another medical condition such as deficient brain growth), and isolated or nonsyndromic (occurring without other anomalies) or syndromic (accompanied by other dysmorphic features or developmental defects). All subclassifications of craniosynostosis can be genetic.² Craniosynostosis of the sagittal suture is the most commonly affected suture and shows a strong male predominance (male:female ratio of 3.5:1). It accounts for 40% to 58% of all cases of craniosynostosis.^{2 6}

Nonsyndromic craniosynostosis (NSC) is usually an isolated abnormality, classified according to the involved suture. Early studies of the epidemiology of simple craniosynostosis noted a predominance of isolated sagittal synostosis, accounting for

Title: Neurodevelopmental Outcomes in Craniosynostosis Repair
PI: [name]
Site: Arkansas Children's Hospital
Funding: UAMS Intramural Grant

more than half of all reported cases. Approximately 85% of cases are believed to be nonsyndromic with no identifiable gene mutation.² Syndromic craniosynostosis, on the other hand, can be associated with various dysmorphic features involving the face, skeleton, or nervous system and may be accompanied by developmental delay.

For specifics of development of neural circuitry, i.e., about 50% of adolescents with NSC experienced some sort of significant cognitive and/or executive planning dysfunction. Abnormal growth can also cause abnormal brain development, particularly in the white matter tracts of the brain. There is also known decreased synaptic branching and myelination in children with syndromic craniosynostosis, as evidenced by Diffusion tensor imaging (DTI).¹⁰

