All these studies must be considered with the following factors. For one thing, it is impossible to separate some of the confounding factors to isolate the causative effect of anesthesia from others, most notably the surgery itself. Two, some other factors such as sex and maternal education have been shown to have a much stronger influence on all measurable neurodevelopmental outcomes than the measurable associations of anesthetic. Many of the other health and social factors that would necessitate multiple surgeries (and anesthetics) for whatever reason, may contribute to a larger extent to these measurable outcomes. Thus, there is mixed evidence at best, that there is a significant risk to neurodevelopmental outcomes of the exposure to general anesthetic in this patient population, particular in this study with a maximum of three additional exposures totaling approximately 90 minutes. This is all the more important to consider in the context that it will be impossible to state whether the child's potential developmental problems, were from the craniosynostosis, the anesthesia or any subsequent anesthetic exposures. It is important to note that the duration of anesthesia in the test subjects undergoing surgery will be anywhere from 2 hours to 5 hours and thus 4-10 times longer than any MRI with sedation they might have after. Moreover, if those patients need sedation they will receive it an older age (i.e. post-op) where there is arguably less change of any further anesthetic exposure affecting development.

Title: Neurodevelopmental Outcomes in Craniosynostosis Repair
PI: [name]
Site: Arkansas Children's Hospital
Funding: UAMS Intramural Grant

As stated, our team will attempt non-pharmacologic calming methods with ALL patients first but will clearly explain to parents the small additional risk of additional MRI's if sedation is necessary. There is a benefit of avoiding the routine use of radiation to diagnose the craniosynostosis, as we would elect to obtain the 'black-bone MRI' pre-operatively which has windowing that emulates the look of a CT scan, enabling easier interpretation.

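### The patient-control comparison of Bayley/Mullen scores is open to confounding by sex and maternal education: controls are stratified by age only, maternal education is not listed for collection, and neither is a prespecified covariate.

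*Combined protocol and SAP*

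**What the plan says.** - **Factors named as influential.** Risks and Benefits states that "some other factors such as sex and maternal education have been shown to have a much stronger influence on all measurable neurodevelopmental outcomes", and the sentence ends with its comparator: "than the measurable associations of anesthetic".
- **Comparison planned.** The Objectives include "neurodevelopmental tests, before and after surgery as compared to age-matched controls". Aim 3 separately relates test results in patients to their white matter changes.
- **Control selection.** Under Inclusion Criteria, controls are "stratified by age groups starting at 3 months", three per band. The Radiological Component adds that "control patients will be stratified by the age when they actually undergo the study not the age of recruitment". No other matching or stratifying factor appears. Study Population gives each control one developmental assessment and one MRI, and expects most to be referrals for positional head shape.
- **Data collected.** The list in Study Design and Procedures includes sex, race, ethnicity and family medical history. It has no maternal education or other socioeconomic item, but it is stated not to be exhaustive.
- **Analysis.** Statistical Methods names t, chi-square and z tests, repeated measures for pre- and post-operative data, and otherwise standard methods. The one covariate it commits to is sedation: "whether or not the participant was sedated will be a variable including in analysis".
- **Sex ratio in patients.** Relevant Literature and Data says sagittal synostosis "shows a strong male predominance (male:female ratio of 3.5:1" and makes up 40% to 58% of cases.

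**The concern.** The plan carries the anesthesia-related variable into the analysis, but neither of the two factors it ranks above anesthesia as influences on developmental scores. One of them, sex, is expected to be unbalanced in the patients by the protocol's own figures. The other may never be recorded.

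At stake is the reading of any patient-control difference in Bayley or Mullen scores. Part of that difference could reflect the sex mix or family background of the two groups rather than craniosynostosis. Enrolling more patients does not reduce such a bias; it only makes the biased estimate look more precise.

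Sex can be added to a model later, because it is collected. Maternal education is more exposed: controls have only one assessment, so an item not asked then can be recovered only by recontact.

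**Working it through.** The plan gives no effect size, SD, alpha or power, so it has no figure of its own to reproduce. The check has two parts: what sex imbalance follows from the protocol's ratios, and what bias that could produce.

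**Inputs from the documents:** sagittal male:female ratio 3.5:1; sagittal share 40% to 58%; up to 500 patients and up to 60 controls.

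**Assumed, not in the documents:** non-sagittal cases 50% male; controls 50% to 65% male; sex effect 0.1 to 0.5 SD; maternal-education gap between groups 10 to 30 points; maternal-education effect 0.2 to 0.6 SD; two-sided 5% test.

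**Step 1, male share**
- Sagittal: 3.5/4.5 = 77.8%.
- Whole cohort, 40% sagittal: 0.40 × 0.778 + 0.60 × 0.50 = 61.1%.
- Whole cohort, 58% sagittal: 0.58 × 0.778 + 0.42 × 0.50 = 66.1%.

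**Step 2, bias in an unadjusted difference** = (difference in prevalence of the factor) × (effect of the factor in SD)
- Sagittal-type mix, controls 50% male: 0.278 × 0.1 = 0.03 SD to 0.278 × 0.5 = 0.14 SD.
- Sagittal-type mix, controls 65% male: 0.128 × 0.1 = 0.01 SD to 0.128 × 0.5 = 0.06 SD.
- Whole cohort, controls 50% male: 0.111 × 0.1 = 0.01 SD to 0.161 × 0.5 = 0.08 SD.
- Whole cohort, controls 65% male: the gap is 61.1 - 65 = -3.9 to 66.1 - 65 = +1.1 points, so the sex bias is at most about 0.02 SD in size (0.039 × 0.5).
- Maternal education: 0.10 × 0.2 = 0.02 SD to 0.30 × 0.6 = 0.18 SD.

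**Step 3, effect on a nominal 5% test.** SE = sqrt(1/n_patients + 1/n_controls) in SD units. Actual type I error = 1 - [Φ(1.96 - b/SE) - Φ(-1.96 - b/SE)], where b is the bias.

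| Comparison | n | SE | Bias (SD) | Type I error |
|---|---|---|---|---|
| Sagittal, controls 50% male | 200 (40% of 500) v 60 | 0.147 | 0.03-0.14 | 5.4%-15.7% |
| Sagittal, controls 50% male | 290 (58% of 500) v 60 | 0.142 | 0.03-0.14 | 5.4%-16.5% |
| Sagittal, controls 65% male | 290 v 60 | 0.142 | 0.01-0.06 | 5.1%-7.4% |
| Whole cohort, sex, controls 50% male | 500 v 60 | 0.137 | 0.01-0.08 | 5.1%-9.1% |
| Whole cohort, maternal education | 500 v 60 | 0.137 | 0.02-0.18 | 5.2%-26.1% |

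The sample sizes are the protocol's ceilings. Smaller groups leave the bias unchanged but raise the SE, so the inflation is smaller.

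**Step 4, which analyses are affected**
- *Patient-control test scores:* directly. The statement about sex and maternal education concerns these outcomes.
- *Patient-control DTI:* not shown. The documents do not say that either factor influences DTI measures.
- *Pre-post change within a child:* fixed level differences cancel. Only a different developmental slope by sex or maternal education could matter.
- *Aim 3 correlation:* it is made within patients, so an imbalance against controls does not bias it. Confounding would need the factor to affect DTI as well as test scores. The more certain gain from adjustment is removal of test-score variance.

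**The case against.** The strongest counter-case has four parts.

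**The ranking is relative.** A reader might infer that the protocol calls sex and maternal education dominant. It does not. It says they outweigh anesthetic associations, which the same section presents as small: school grades 0.41% lower, IQ 0.97% lower, and a non-significant 1.3 IQ points. No absolute effect is given. This stands, and it is why every effect above is assumed.

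**The imaging endpoints are not implicated.** A reader might extend the point to the DTI comparisons, to the effect of surgery, or to Aim 3 through the control imbalance. The documents do not support these extensions, for the reasons in Step 4. This stands and limits the point to the patient-control test scores, with a lesser gain in precision for Aim 3.

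**Silence is not exclusion.** The data list is open-ended, biostatistical support is planned, and standard methods could include adjustment. It would be wrong to say that maternal education will not be collected or can never be adjusted for: patients can be asked at a later visit and controls can be recontacted. But nothing commits the study to doing so.

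**The bias may be small.** The controls' sex mix is unknown, and if they are about 65% male the whole-cohort sex bias nearly vanishes. Even at 50% male, its upper value of 0.08 SD is below the SE of 0.137 SD. This stands for sex. For maternal education the documents give no information on the gap in either direction. The within-normal-limits screen that controls must pass before MRI could itself create a gap if maternal education affects scores.

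**Conclusion.** The point holds for the patient-control comparison of Bayley/Mullen scores. The protocol names two influences on those scores, selects controls without regard to either, does not list one of them for collection, and prespecifies adjustment for neither. A sex imbalance is foreseeable from its own figures, unless controls happen to be similarly male-heavy.

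The size is illustrative: 0.01-0.14 SD for sex in a sagittal-type mix and 0.02-0.18 SD for maternal education. Only the patient sex ratio, the sagittal share and the group-size ceilings come from the documents; the rest is assumed. The direction of the bias cannot be stated. The change is worth making because it is cheap now, and harder for controls once their only assessment has passed.

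**What to change.** 1. Add maternal education (one question) to the data list for patients and controls. Ask controls at their single assessment and patients already enrolled at their next visit. Recontact controls already seen before the master key is destroyed, which the data-handling section schedules for after publication.
2. In Statistical Methods, prespecify age, sex and maternal education as covariates in the patient-control and DTI-cognition models, alongside sedation where MRI measures are analysed.
3. If published data replace enrolled controls, as the Control Group Neurodevelopmental Assessment section allows, check that sex and maternal education are available there in comparable form, and state the limitation if they are not.

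Matching controls on sex is optional, because sex is recorded and model adjustment suffices. Adjustment does not undo the selection of controls on their own test scores by the normality screen; that needs separate handling.

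The cost is one added question, a few recontacts and two extra model terms (sex and maternal education). No clinical procedure changes.
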